### Monitoring Period

#### **Group 1**

Group 1 will continue on their standard diabetes care. At 4 months they will perform a 20 day period of blinded CGM monitoring. This will require them to insert the CGM device on two occasions during this 20 day period. During this 20 day period this group will continue on their standard diabetes care, including monitoring their own blood glucose, as they will not be able to view the data from the CGM device. Participants in this group will perform a further 20 day period of blinded CGM monitoring prior to the second hypoglycaemic clamp study. This means that participants in this group will have to insert the CGM device on 6 occasions during the study period. In each of these periods of blinded CGM monitoring the aim will be to collect at least 14 days of data. Study staff will collect the CGM devices at the end of each 20 day blinded period so that the data can be downloaded for analysis. CGM devices for these two blinded periods will be delivered to the participants' home. The device for the 4 month period will then be collected from the participant by study staff. The device used prior to the second clamp study can be given to study staff at the clamp study visit. During each of these blinded CGM periods participants will be asked to complete a 7-day food diary, to include 5 week days and 2 weekend days. This can be in the form of a paper diary provided by study staff or a mobile phone application. This can be returned to study staff at the next visit or by post, a stamped addressed envelope will be provided. After the second clamp study participants will be invited to take part in a 3-month study extension phase. During this time they will be converted to the study devices. They will be asked to upload their study pump once a week and will have ad hoc contact with the investigators over this time to adjust pump settings as required. At the end of the 3 months they will be sent quality of life questionnaires to complete along with a stamped addressed envelope to return these to the investigators.

#### **Group 2**

Participants in group 2 will be continually monitored throughout the study period to ensure time in range is optimised throughout the 8 months. They will be asked to upload their insulin pump data at least once weekly to the online platform Tandem t:connect. This is done using a USB device provided with the insulin pump and the participants own computer or laptop with internet access. Participants will be given training in the use of the platform and account logins as part of their pump training. The data from the participant's CGM device will also be reviewed by study staff. This data automatically uploads to the Dexcom Clarity cloud platform without the need for the participant to physically attach the device to their computer. Study staff will review blood glucose data on Dexcom clarity daily to ensure time in range is being maximised.

Study staff will review the uploaded pump data at least once weekly using administrative log-in details and will contact participants by telephone if the data suggests:

1. Adjustments are required to insulin pump settings (carbohydrate ratios, insulin sensitivity factor, basal rates) as they are experiencing time out of the target glycaemic range
2. The participant is not changing the insulin pump set every 3 days
3. The participant requires further education about the low carbohydrate diet or carbohydrate counting

4. The participant is experiencing multiple alarms or error codes

Participants will have contact information for study staff and will be able to contact staff via email or telephone on an ad hoc basis throughout the study.

### **Study Visit 6**

A scheduled mid-point telephone consultation at 3-4 months will be arranged for all participants. This can be a face-to-face appointment if requested by the participant. All participants will also have a HbA1c measured at 4 months. This will be done using a home testing kit provided by Exeter Clinical Laboratory International if participants decide to have a telephone visit. Samples are collected via a fingerstick blood test, in the same manner as checking a blood glucose, and then posted to the reference lab in Exeter for sample analysis. If the participant decided to have a face-to-face visit a laboratory HbA1c will be taken in place of the home testing kit.

Participants in group 2 will be asked to attend for repeat retinopathy screening at 3-4 months.

### **Study Visit 7: Hypoglycaemic Clamp Study**

All participants will undergo a second hypoglycaemic clamp study, as previously described, at 8 months. Participants will be given the following questionnaires to complete.

1. EQ5D
2. Fear of Hypoglycaemic Scale
3. Hypoglycaemic Confidence
4. Diabetes Technology Attitudes
5. Diabetes Specific Emotional Distress (DDS-1)
6. Diabetes Treatment Satisfaction Questionnaire
7. Gold Score

Participants will return their study devices. They will be given the opportunity to discuss the study with study staff and provide any feedback.

### **Study Visit 8 (Group 1 only)**

Participants in group 1 who have agreed to take part in the 3-month study extension phase will attend for training on using the Dexcom CGM along with the Tandem t:slim X2 insulin pump. This session will take a variable amount of time depending on if the participant was on an insulin pump prior to the study.

After this visit participants will have ad hoc telephone contact with investigators to review insulin pump setting or provide advice regarding the devices. They will be asked to upload their pump once weekly to the t:connect platform. They will be sent the following questionnaires to complete at home after 3 months (+/- 2 weeks) which they will return to the investigators in a stamped addressed envelope:

1. EQ5D
2. Fear of Hypoglycaemic Scale

[figure not shown]
3. Hypoglycaemic Confidence
4. Diabetes Technology Attitudes
5. Diabetes Specific Emotional Distress (DDS-1)
6. Diabetes Treatment Satisfaction Questionnaire
7. Gold Score

All participants will undergo repeat retinopathy screening at the end of the trial period.

Table 1: Study Procedures

Assessment	Study Preparation					Study				3 Month Extension Phase	
	Visit 1- Screening	Visit 2- Baseline	Visit 3 (Group 2 only)	Up To 2-week Study run-in	Visit 4 (Group 2 only)	Visit 5 (Study start)	Visit 6 (4 months)	Visit 7 (8 months)	Visit 8 (Group 1 only)	Visit 9 (Group 1 only)	
Eligibility Assessment	X										
Written informed consent	X										
Demographic data, contact details	X										
Weight	X					X		X			
Height	X					X		X			
BMI	X										
Pregnancy Test	X					X		X			
Food diary, 7 days		X					X (Group 1)	X (Group 1)			
Vital signs: heart rate, blood pressure	X					X		X			
Questionnaires		X				X		X			X (returned by post)
Medical History	X										
Urine sample: <del>Albumin/creatinine ratio</del>	X										
Retinal Screening	X						X (Group 2)	X			
Spot HbA1c	X						X	X			
HbA1c	X							X			
Hypoglycaemic Clamp Study						X		X			
ALL- Blinded CGM for 20 days		X									
ALL- telephone review							X				
All- return study devices								X			
GROUP 1- Blinded CGM for 20 days							X	X			
Fitting of t:slim X2			X						X (if not previously on pump, otherwise CGM fitting only)		
Group 2- pump check-list					X						
GROUP 2- Use of pump and CGM device in unblinded mode					→						
Group 2- Low carbohydrate diet					→						
Group 1- Use of pump and CGM device in unblinded mode					→						
Review- telephone or face-to-face as required	→										

Figure 3: Study Flowchart

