### 2.2.2 Secondary Endpoints

Treatment satisfaction, fear of hypoglycaemia and quality of life at baseline compared to endpoint using validated questionnaires. Changes in endogenous glucose production and glycerol kinetics as measured by stable isotope studies. The difference in time in range and QoL between participants using the HCL system and following the LCD and those using the HCL system alone will be compared.

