- Consume a moderate carbohydrate (40-60g) evening meal the night before
- Fast for at least 8 hours before presenting to the clinical research facility at 07:00 (participant can continue to consume water as required)
- Avoid hypoglycaemia- the study will be postponed if the blood glucose is <3mmol/l for >20 minutes
- If on basal/bolus or open loop pump system to reduce their basal insulin the night before by 20%
- If on a closed loop system to place the pump on exercise settings the morning of testing

The clamp study will be rescheduled if the participant has donated blood in the preceding 12 weeks if male and the preceding 16 weeks if female.

When participants arrive in the ERICRF they will have anthropological measurements taken to calculate their infusion rates accurately. They will also have a pregnancy test if applicable.

Two peripheral intravenous cannulas will be inserted. The first of these will be in the nondominant hand which will then be placed in a heated box at 55°C to aterialise venous blood. This will be used for blood sampling during the study. The second cannula will be inserted an antecubital fossa vein for the infusions. At the time of cannula insertion baseline bloods will be obtained for: glucose, glycerol, D2 Glucose, D5 Glycerol, Free Fatty Acids, lipid profile, insulin, glucagon, cortisol, adrenaline and noradrenaline. Note that bloods for D2-Glucose and D5-Glycerol will only be taken when the investigators have received supply of the isotopes. There is currently a delay in this supply and the investigators anticipate receiving the isotopes in January 2022. Clamp studies carried out before receipt of the isotopes will not have these samples taken.

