## 9.2 PROPOSED ANALYSES

In primary analyses, the glucagon response to insulin induced hypoglycaemia at 0 and 8 months will be compared to the individual's baseline glucagon responses within each group. In further exploratory analyses, the participants in the highest tertile of glycaemic TIR as a group over the 8 months will be compared to those in the lowest tertile over the 8 months as a

group. The rate of appearance (Ra) of the stable isotopes will be used as a marker of endogenous glucose production. Analysis of tracee:tracer ratio will be made by mass spectrometry. The TIR of participants completing the study 3-month extensions will be compared to that of group 2 during the study.

We predict minimizing exposure of alpha cells to hyperglycemia with AID +/- VLCD should significantly enhance glucagon.

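### Table 1 and the protocol text disagree on whether extension participants already on a pump receive the t:slim X2, and section 9.2 does not define the HCL-alone group by device

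*Combined protocol and SAP*

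**What the plan says.** The documents describe the extension devices in two ways.

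- **Table 1 (section 6.1), t:slim X2 fitting row, Visit 8:** "X (if not previously on pump, otherwise CGM fitting only". Read literally, someone already on a pump is given a sensor and no study pump. The Visit 3 entry for Group 2 in the same row carries no such condition.
- **Synopsis, treatment groups:** the control group is moved to the t:slim X2 with Control-IQ and Dexcom CGM for the extension, with no exception.
- **Section 6.1, Monitoring Period, Group 1:** "During this time they will be converted to the study devices". The same paragraph adds "They will be asked to upload their study pump once a week".
- **Section 6.1, Study Visit 8:** those who join "will attend for training on using the Dexcom CGM along with the Tandem t:slim X2 insulin pump". Prior pump use affects only how long this takes: "This session will take a variable amount of time depending on if the participant was on an insulin pump prior to the study".

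Two places use the extension data. Section 2.2.2 says that TIR and quality of life (QoL) in participants on the HCL system with the low-carbohydrate diet and in "those using the HCL system alone will be compared". Section 9.2 says "The TIR of participants completing the study 3-month extensions will be compared to that of group 2 during the study". Section 9.2 does not refer to the device worn.

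**The concern.** The secondary comparison is meant to set closed loop plus diet against closed loop without the diet, so everyone on the second side needs to have been given closed loop. If site staff worked from the Table 1 cell, a prior user of another open-loop pump would have a sensor and that pump, with no automated delivery. Section 9.2 would still count that person as an extension completer. Because closed loop is expected to raise TIR, the HCL-alone mean would fall and the gap to Group 2 would look larger than it is. With at most a dozen or so people on that side, one person could move the mean visibly.

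**Working it through.** The plan states no figure for this comparison, and section 9.1 justifies the sample size by precedent only, so there is nothing to reproduce. The check is one of consistency, followed by an illustration.

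**Step 1: can the affected people be enrolled?** Yes.
- Section 4.3 excludes non-approved closed-loop systems and predictive low-glucose-suspend pumps. Ordinary open-loop pumps are not listed. It also excludes recent regular real-time CGM use, so most prior pump users would be open-loop.
- The clamp preparation in section 6.1 (Study Visit 5) provides for them: "If on basal/bolus or open loop pump system to reduce their basal insulin the night before by 20" per cent.
- Section 4.1 recruits from the type 1 clinic as well as the pump waiting list. Section 13.6 mentions only the waiting list, which points to few prior pump users. The Visit 8 text nevertheless expects some.

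**Step 2: would a sensor alone give closed loop?** Not with a different pump. Sections 1.1 and 3 place the Control-IQ algorithm inside the t:slim X2. Section 13.6 says this pump is one of several offered locally, so a prior pump user may or may not already have it.

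**Step 3: which analysis statement would miscount?** Section 2.2.2 limits the comparator to people using the HCL system, so a person without closed loop falls outside it. Section 9.2 takes all extension completers. The two agree only if every completer had closed loop.

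**Step 4: illustration of size.** Inputs from section 1.1: TIR 71% on Control-IQ and 59% on sensor-augmented open-loop pump. Let f be the share of extension participants left on another open-loop pump.

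Expected HCL-alone mean = 71 − f × (71 − 59) = 71 − 12f

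| Extension participants (assumed) | Prior users of another pump (assumed) | f | Fall in mean, points | Mean TIR, % |
|---|---|---|---|---|
| any | 0 | 0 | 0 | 71 |
| 12 | 1 | 1/12 | 1.0 | 70.0 |
| 12 | 3 | 3/12 | 3.0 | 68.0 |
| 12 | 6 | 6/12 | 6.0 | 65.0 |
| 3 | 1 | 1/3 | 4.0 | 67.0 |
| any | all | 1 | 12 | 59 |

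Twelve is half of the planned 24, with everyone joining. Three is the number in Group 1 at the September 2022 amendment (section 6.1, Randomisation). Neither is a stated extension size.

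Section 1.1 also gives the closed-loop baseline as 61%, with control unchanged at 59%. The difference in change is (71 − 61) − (59 − 59) = 10 points. On that basis the fall is 10f: 0.8 points for one person in 12 and 3.3 for one in 3.

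**The case against.** The strongest reply is that one table cell stands against the rest of the protocol. Conversion to the study devices appears without exception in the synopsis, section 3, the randomisation text and the Group 1 text. Table 1 has its own row for Group 1 using pump and CGM unblinded, with no prior-pump condition. Extension participants upload weekly to t:connect (section 6.1, Visit 8, and section 7), which the protocol describes as the platform for the Tandem pump. A person left on another maker's pump does not fit that data flow. The cell may also be shorthand for someone already wearing a t:slim X2, or for no new pump start.

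Much of this stands. A reader might infer from the cell that prior pump users will be counted as closed-loop users without having closed loop. The documents do not support that as a forecast: it follows only if staff act on the cell and not on the text. What remains is that no rule says which prevails, and that the cell refers to being on a pump, not on this pump.

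A reader might also credit any resulting shift in TIR entirely to the diet. That is too strong. The two sides also differ in duration (3 against 8 months), in support (ad hoc contact against daily CGM review) and, from protocol version 8, in allocation, which is no longer randomised. Correcting the cell would not by itself isolate the diet.

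**Conclusion.** The point holds as an internal contradiction with a conditional consequence. Table 1 and the text of section 6.1 and the synopsis cannot both be followed for a prior user of a different pump, and section 9.2 has no device-based definition that would catch the result. If the cell were followed, the direction is known: HCL-alone TIR would be lowered and the gap to Group 2 widened in favour of the diet arm. The size cannot be fixed. It is 10f to 12f points, where f is unknown and the TIR figures come from the trials quoted in section 1.1. If the text is followed, f is 0 and there is no effect. No direction or size can be derived for QoL.

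Only the secondary comparison in an optional extension is at risk. The primary glucagon endpoint is measured at the two clamps, before Visit 8, and is untouched. The contradiction is worth correcting because the change is cheap and the group is small.

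**What to change.** 1. Reconcile the Visit 8 cell of Table 1 with the synopsis and with the Group 1 and Visit 8 text of section 6.1. State whether the cell means people already wearing a t:slim X2. Which text stands is for the sponsor to decide.
2. Record for each extension participant the pump and closed-loop system fitted.
3. In section 9.2, define the HCL-alone group as extension participants fitted with the t:slim X2 with Control-IQ. Define it by device provided and apply the same rule to Group 2. Report anyone given CGM only separately.

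The definition should not rest on Control-IQ being active in the extension group alone. That would select on use on one side only and could bias the comparison the other way.

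The cost is one table cell, one recorded item and one sentence in 9.2. The downside is a slightly smaller HCL-alone group if anyone received CGM only.

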## 6.2 STORAGE AND ANALYSIS OF SAMPLES

The blood tests set out in the table below will be required during the study. The volumes represent the volume required during the whole trial.

Test	Container	Volume Required (ml)	Number of Tests	Total Volume
Screening Visit				
HbA1c	EDTA	1ml	1	
HbA1c spot	Testing kit	0.5ml	1	
FBC	EDTA	2ml	1	
Urea and Electrolytes	LithHep	5ml	1	
Thyroid Function	LithHep	5ml	1	
Pregnancy Test (urine)	n/a	n/a	1	n/a
Total Volume				13.5ml
Clamp Study 1				
Glucagon	EDTA	3ml	10	30ml
Cortisol	Serum	3ml	10	30ml
Adrenaline	LithHep	3ml	10	30ml
Noradrenaline	LithHep	3ml	10	30ml
Insulin	LithHep	3ml	10	30ml
Glucose	Fluoride	1ml	48	48ml
Glucose (near-patient test)	n/a	0.5ml	48	24ml
Glycerol	Plasma	2ml	13	26ml
Free Fatty Acids	Fluoride	2ml	10	20ml
D2 Glucose	Plasma	1ml	13	13ml
D5 Glycerol (only in study visits when supply available)	Plasma	1ml	13	13ml
Lipid profile	Serum	4ml	1	4ml
Pregnancy Test (urine)	n/a	n/a	1	n/a
Total Volume				298ml
4 Month Test				
HbA1c Spot (telephone visit)	Testing kit	0.5ml	1	0.5ml
HbA1c (face-to-face visit)	EDTA	1ml	1	1ml
Clamp Study 2				
Glucagon	EDTA	3ml	10	30ml
Cortisol	Serum	3ml	10	30ml
Adrenaline	LithHep	3ml	10	30ml
Noradrenaline	LithHep	3ml	10	30ml
Insulin	LithHep	3ml	10	30ml
Glucose	Fluoride	1ml	48	48ml
Glucose (near-patient test)	n/a	0.5ml	48	24ml
Glycerol	Plasma	2ml	13	26ml
Free Fatty Acids	Fluoride	2ml	10	20ml
D2 Glucose	Plasma	1ml	13	13ml
D5 Glycerol	Plasma	1ml	13	13ml
Lipid profile	Serum	4ml	1	4ml

Pregnancy Test (urine)	n/a	n/a	1	n/a
HbA1c Spot	Testing kit	0.5ml	1	0.5ml
HbA1c	EDTA	1ml	1	1ml
Total Volume				299.5ml
Volume for all tests (maximum):				611ml

The measurement of blood glucose during the clamp study is critical for the safety of the participants and integral to the study itself. Without this we would not know if a participant was at the desired blood glucose level. Measurement of glucagon during the clamp study is key to determining the primary outcome of the trial- the glucagon response to hypoglycaemia. Other hormones that are involved in the body's response to hypoglycaemia will also be measured during the clamp study (adrenaline, noradrenaline and cortisol). While these are not directly related to the primary outcome of the trial they are linked as the intervention may show an improvement in these responses. An improvement in these responses is also linked to improvement in awareness of hypoglycaemia, which is a secondary outcome measure for the trial for those with IAH. This trial is looking at time in range as a measure of blood glucose control in type 1 diabetes. This is an emerging tool for measuring control in diabetes that has only been made possible in recent years through new technologies such as CGM. Traditionally HbA1c is used as a measure of blood glucose control. That is why participants will have this measured at baseline, midpoint and endpoint. The HbA1c blood spot samples will not be analysed locally. They will be sent to a reference lab in Exeter for analysis (Exeter Clinical Laboratory International, Royal Devon and Exeter NHS Trust, Exeter).

The blood taken during the screening visit and the lipid profile taken during the clamp studies are part of the standard monitoring of people with type 1 diabetes.

During the trial period participant blood samples will be stored in the ERICRF. The blood samples will be stored in a secure and monitored environment and will be disposed of according to the Human Tissue Authority's code of practice after a period of 5 years.

## 7 DATA COLLECTION

During the trial data will be collected by study staff. The following data will be collected at these time points:

1. Selection of potential participants prior to consent:
  - a. Review of electronic health care records, Trakcare and SCI Diabetes, for exclusion criteria
  - b. This data will be reviewed by study staff who are part of the participant's healthcare team
2. Eligibility Assessment (after obtaining written informed consent):
  - a. Inclusion and exclusion criteria assessment.
  - b. Demographics (date of birth, sex, race and ethnicity)

- c. Contact information (retained at the site and not entered into study database)
  - d. Medical history
  - e. Concomitant medications
  - f. Pregnancy test if applicable
  - g. HbA1c blood test
  - h. Bloods test for : Renal function and thyroid function
  - i. Urine sample for albumin:creatinine ratio
  - j. Physical examination to include: Weight, height, BMI, vital signs including measurement of blood pressure and heart rate
  - k. Modified gold score
  - l. Retinal screening will be arranged if this has not occurred in the previous 6 months
3. Baseline:
- a. CGM Data:
    - i. All participants will have blinded CGM data collected over a 20 day period (aiming to capture at least 14 days of data)
    - ii. This data will be collected automatically by the device after being fitted by the participant before being uploaded to a secure cloud-based platform
  - b. All participants will complete the study questionnaires:
    - i. Quality of life: EQ5D, Diabetes Specific Emotional Distress (DDS-1)
    - ii. Treatment satisfaction: Diabetes treatment satisfaction questionnaire
    - iii. Technology: Diabetes technology attitudes
    - iv. Fear of hypoglycaemia: Hypoglycaemia confidence, Fear of Hypoglycaemic Scale
  - c. All participants- first hypoglycaemic clamp study
4. Trial period
- a. Participants in group 2 will have data collected from their insulin pump and CGM device
  - b. Insulin pump data will be uploaded by the participant at least once per week to the secure platform Tandem t:connect
  - c. CGM data will be automatically uploaded to the secure cloud-based platform Dexcom Clarity
5. Midpoint
- a. Participants in group 1 will undergo a further 20 day period of blinded CGM data collection
  - b. All participants will have blood taken for HbA1c
6. Endpoint:
- a. Participants in group 1 will undergo a further 20 day period of blinded CGM data collection
  - b. All participants will complete the study questionnaires:

- i. Quality of life
  - ii. Treatment satisfaction
  - iii. Technology
  - iv. Fear of hypoglycaemia
  - c. All participants- second hypoglycaemic clamp study
7. Study extension phase (3 months)
- a. Participants in group 1 who agree to the extension phase will have data collected from their pump and CGM device
  - b. Insulin pump data will be uploaded once weekly to the Tandem t:connect
  - c. CGM data will be automatically uploaded to the secure cloud-based platform Dexcom Clarity
  - d. The following questionnaires will be completed:
    - i. EQ5D
    - ii. Fear of Hypoglycaemic Scale
    - iii. Hypoglycaemic Confidence
    - iv. Diabetes Technology Attitudes
    - v. Diabetes Specific Emotional Distress (DDS-1)
    - vi. Diabetes Treatment Satisfaction Questionnaire
    - vii. Gold Score

Participants will be given different options for completing the questionnaires related to the trial. They can be completed while at a visit with study staff, can be taken home and returned to staff by post or handed to study staff at the next visit.

